### 6.2 Analysis Methods

#### 6.2.1 Analysis of primary feasibility outcome

The **completion rate** (proportion of patients who swallow the sponge and have it retrieved without additional intervention) will be presented together with the corresponding 95% confidence interval. Participants who have attempted to swallow the Cytosponge™ are evaluable for the primary endpoint. Those who are not evaluable may be replaced at the Chief Investigator’s discretion.

## 6.2.2 Analysis of secondary feasibility outcomes

### Safety

All Adverse Events (AEs) and Serious Adverse Events (SAEs) will be summarised using the safety population. As the Cytosponge™ is an Investigational Medical Device, additional adverse event categorisation – of Adverse Device Effect (ADE), Serious Adverse Device Effect (SADE), and Unanticipated Serious Adverse Device Effect (USADE) – is required. Serious Adverse Events related to the procedure and any events recorded as ADE, SADE, or USADE will be summarised over the follow-up period i.e. from the time of Cytosponge™ administration (D1) until the patient completes the study at the two week telephone follow-up, or until the time of surgery if the patient is operated on within the follow-up period.

Telephone follow-up interviews will not be undertaken after surgery. If an Investigator reports any study intervention related SADEs following the two week follow up period (as noted in Protocol V3.0), these will also be included in the summaries. Summaries will be in tabular form. It is intended that the number and percentage of patients experiencing SAEs overall, will be presented by treatment group (naCRT/dCRT). SAEs, SADEs, and USADEs will be grouped by system organ class (SOC) and according to whether they occurred on the day of the procedure or later.

In addition, all AEs and ADEs will be summarised in tabular form. It is intended that the number and percentage of patients experiencing AEs and ADEs will be presented overall and according to causality (treatment-relatedness). The AEs may be split by grade (1-2 and 3+) and presented by SOC and according to whether they occurred on the day of the procedure or later. These descriptive summaries will be based on the safety population.

**Consent rate** (agreement to undergo procedure), defined as the percentage of eligible patients who consent to participate in the study. Any patients who consent but withdraw their consent prior to the Cytosponge™ procedure will be considered not to have consented. The percentage will be presented together with the corresponding 95% confidence interval.

**Acceptance rate** (acceptance to repeat procedure), defined as the percentage of patients who have successfully undergone the Cytosponge™ procedure and would be prepared to accept the procedure repeatedly if it was to be used for follow-up. A questionnaire will be given to each patient, to be completed after the procedure. The questionnaire will either be completed just after the procedure or, if the patient cannot stay, completed later and returned by post.

**Suitability of sample for biomarker analysis**, defined as the percentage of samples from the Cytosponge™ test with the presence of cytological atypia and/or p53 abnormality (also called “positive samples”). Quality of material obtained from the Cytosponge™ test will be centrally analysed at Cambridge. Cellularity, yield and quality of extracted DNA will be used as measure of quality. Data for these analyses are not expected to be available with the data for the primary outcome and the acceptance- and safety-related secondary outcomes; biomarker analyses will therefore be conducted and reported separately.

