Exclusion criteria	
 1. Known to have oesophageal varices or stricture requiring dilatation of the oesophagus 2. Unable to temporarily discontinue anticoagulation therapy/medication prior to their procedure* 3. Oesophageal stent 4. Other psychological, social or medical condition, physical examination finding or a laboratory abnormality that the Investigator considers would make the patient a poor study candidate or could interfere with protocol compliance or the interpretation of study results. 
* Patients on anti-coagulation therapy are eligible for the study as long as they are considered suitable candidates for endoscopic biopsy (follow local hospital procedures for management of patients on anticoagulation due to undergo endoscopy). If temporary discontinuation of anticoagulation is required, this should be after consultation with the patients clinical care team.

Study intervention and administration	Cytosponge™ test kit, is a Class I, single-use, non-sterile, non CE-marked device that consists of an expandable spherical 3cm diameter mesh, encapsulated in a gelatine capsule, which is attached to a cord. The capsule is swallowed and allowed to reach the stomach while remaining attached to the cord. All patients will undergo Cytosponge™ test at one time-point 4-16 weeks after completion of CRT.
Duration on study	Approximately 1 month
Patient care post-study	Following the end of study visit, patients will receive standard care.
No. of Study Site(s)	UK multicentre trial; Approximately 10 sites.
End of study	Last Patient Last Visit (including telephone follow up).

SUMMARY OF EVENTS

	During or post routine CRT	Pre-study intervention	Cytosponge™ procedure	Telephone follow up ⁵	Telephone follow up ⁵
	At least 24 hours before consent	Ideally on D1 where possible, otherwise within 7 day period preceding procedure	D1	1 week (+/-2days) post Cytosponge™ procedure	2 weeks (+/-2 days) post Cytosponge™ procedure
PIS provided to potential participant	X				
Inclusion / exclusion criteria confirmation ¹		X			
Written informed consent		X			
Study Registration		X			
Demographics		X			
Medical history: 
 Clinically significant disease history Prior treatment Comorbidities 		X			
Concomitant medications		X		X	X
Physical examination ² including vital signs		X			
WHO Performance Status		X			
Dysphagia score		X	X	X	X
Cytosponge™ procedure*			X		
Safety monitoring ³			X	X	X
Questionnaire ⁴			X		

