Research Bloods (optional)			X		

¹ Refer to re-screening section 4.4

² See section 5.2

³ Week 1 and Week 2 safety monitoring will be undertaken by telephone call

⁴ Questionnaire administered post procedure to those who successfully complete the procedure. This can be returned in the post if the participant is unable to stay.

⁵ Only applicable for participants that have received definitive CRT, or for participants who have received neo-adjuvant CRT, if these times are prior to surgery.

*Cytosponge™ procedure will be performed 4-16 weeks after completion of CRT. Refer to section 5.3 & 8.1

-If patient has received definitive CRT, and endoscopy and biopsy is being performed to assess response to CRT (as part of routine procedure for centre), aim to perform Cytosponge™ ideally on the same day or within a week preceding endoscopy to allow collection of matched samples for analysis.

-If patient has received neo-adjuvant CRT, aim to perform Cytosponge™ on the same day or within a week prior to surgery, to allow collection of matched samples for analysis.

ABBREVIATIONS

AE	Adverse Event	MHRA	Medicines and Healthcare products Regulatory Authority
ADE	Adverse Device Effect	medDRA	Medical Dictionary for Regulatory Activities
BE	Barrett's oEsophagus	naCRT	Neo-adjuvant Chemoradiotherapy
BP	Blood Pressure	NIHR	National Institute for Health Research
CI	Chief Investigator	OCTO	Oncology Clinical Trials Office
CTA	Clinical Trials Agreement	OS	Overall Survival
CTAAC	Clinical Trials Awards and Advisory Committee	pCR	Complete pathological response
CRT	Chemoradiotherapy	PI	Principle Investigator
dCRT	Definitive Chemoradiotherapy	PIS	Patient Information Sheet
DSMC	Data and Safety Monitoring Committee	REC	Research Ethics Committee
eCRF	Electronic Case Report Form	RSI	Reference Safety Information
GCP	Good Clinical Practice	SADE	Serious Adverse Device Effect
GI	Gastrointestinal	SAE	Serious Adverse Event
GLP	Good Laboratory Practice	SCC	Squamous Cell Cancer
GP	General Practitioner	SOP	Standard Operating Procedure
HRA	Health Research Authority	TFF3	TreFoil Factor 3
HTA	Human Tissue Act	TMG	Trial Management Group
IMP	Investigational Medicinal Product	USADE	Unanticipated Serious Adverse Device Effect
ISRCTN	International Standard Randomised Controlled Trials Number	WHO	World Health Organisation
LPLV	Last Patient Last Visit		

1 INTRODUCTION**1.1 Background**

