8.3 Special precautions

The Cytosponge™ is not CE marked and not authorised for use in the UK. The trial will be conducted under a Notification of No Objection from the MHRA.

If the Cytosponge™ detaches from the string or if the Cytosponge™ cannot be removed, the recommended approach is to remove the Cytosponge™ by endoscopy ideally within 3 hours of the ingestion. Therefore, where patients are

planned to have re-assessment endoscopy for detection of response to dCRT, the Cytosponge™ procedure should be undertaken prior to endoscopy for logistic reasons. Similarly, for patients who have undergone naCRT, the procedure should be performed on the day of surgery prior to the operation (but this is not mandatory).

Pregnancy is not a contraindication to the Cytosponge™, however, endoscopy is generally avoided in pregnant women. Sites should ensure that participants are able to receive endoscopy in accordance with their local practices in the event this is required. This may include excluding those who are pregnant depending on local endoscopy guidelines. Many of the patients enrolled in this study will be required to undergo endoscopy in standard care, and when applicable, will be informed for their routine care procedure and via the CYTOFLOC PIS, that endoscopy is not advised for pregnant women.

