11 ASSESSMENT OF SAFETY

There are no Investigational Medicinal Products (IMPs) in this trial. The only study-specific interventional procedure is the investigational Cytosponge™ procedure, which will comply with the MHRA Medical Device Directive.

The Investigator will monitor each patient for clinical evidence of Adverse Events (AEs) & Serious Adverse Events (SAEs) on a routine basis throughout the study. The Cytosponge™ is an Investigational Medical Device & therefore additional categorisation of Adverse Device Effect (ADE) and Serious Adverse Device Effect (SADE) is required. Adverse Event monitoring starts from the time of Cytosponge™ administration until the participant completes the study at the Two Week Telephone Follow Up appointment. If a participant receives surgery prior to their two week follow up visit, then their safety reporting period will be up until they receive surgery (see section 5.3, Telephone Follow-Up Evaluations (End of Study)). Should an Investigator become aware of any study intervention related SADEs following the Two Week Telephone Follow Up, these must also be reported as stated below. All reportable AEs will be followed to a satisfactory conclusion.

All AEs reported to the Trial Office will be processed according to internal SOPs. The Trial Office may request additional information for any AE as judged necessary.

The study team will keep in close communication with the manufacturer Cambridge University Hospitals including in the case of a serious adverse device effect, device deficiencies and other quality control aspects. Main quality and safety issues will be reported via email to Cambridge University Hospital within 48 hours of the sponsor becoming aware. No patient identifiable information will be disclosed to the manufacturer at any time.

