### 4.2 Definition of Analysis Populations

**Population for assessment of completion rate:** all patients who have provided consent and have attempted to swallow the Cytosponge™.

**Population for calculation of consent rate:** all patients who consented, out of all those patients who were eligible.

**Population for assessment of acceptance rate:** all patients who successfully undergo the Cytosponge™ procedure.

[figure not shown]
**Population for assessment of suitability of sample:** all samples (taken during the Cytosponge™ procedure) sent to Cambridge for analysis.

**Safety population:** all participants who attempted to swallow the Cytosponge™.

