#### 6.1.2 Secondary feasibility outcomes

**Safety:** defined as all serious adverse events (including bleeding requiring transfusion and perforation) that occur between from the time of Cytosponge™ administration (D1) and when the patient completes the study at the two week telephone follow-up. If a participant undergoes surgery prior to their two week follow up visit, then their safety reporting period continues until the time of surgery. Adverse events will also be reported. Severity rating of adverse effects will be as per the Common Terminology Criteria for Adverse Events (CTCAE) V4.03.

**Consent rate:** defined as the proportion of eligible patients who consent to take part in the study.

**Acceptance rate:** defined as the proportion of patients who have successfully undergone the Cytosponge™ procedure and would be prepared to accept the procedure repeatedly if it was to be used for follow-up.

**Suitability of sample for biomarker analysis:** defined as the percentage of samples from the Cytosponge™ test with the presence of cytological atypia and/or p53 abnormality (also called “positive samples”).

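### The by-group SAE percentages use all attempters as denominator over unequal follow-up windows, so at equal risk the naCRT figure is expected to equal or fall below the dCRT figure

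*SAP*

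**What the plan says.** **Table and denominator.** SAP 6.2.2 (Safety) states: "It is intended that the number and percentage of patients experiencing SAEs overall, will be presented by treatment group (naCRT/dCRT". These summaries use the safety population, which SAP 4.2 defines as "all participants who attempted to swallow the Cytosponge™".

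**Window.** The last planned safety contact in the Protocol's Summary of Events is the telephone call at "2 weeks (+/-2 days) post Cytosponge™ procedure", that is, day 12 to 16. For patients operated on earlier, SAP 6.1.2 says: "If a participant undergoes surgery prior to their two week follow up visit, then their safety reporting period continues until the time of surgery". Protocol section 11 has the same rule: "then their safety reporting period will be up until they receive surgery".

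**Timing of the next procedure.** For naCRT, the Summary of Events footnote says "aim to perform Cytosponge™ on the same day or within a week prior to surgery", and Protocol 8.3 says "the procedure should be performed on the day of surgery prior to the operation (but this is not mandatory". For dCRT, where endoscopy and biopsy are the centre's routine response assessment, the footnote says "aim to perform Cytosponge™ ideally on the same day or within a week preceding endoscopy".

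**Handling of the shortened follow-up.** SAP 6.3 acknowledges that operated patients have no serious adverse effect data after surgery, and plans no imputation. SAP 5.5 will count patients who have the one- and two-week interviews. SAP 6.2.2 also groups SAEs by whether they fell on the procedure day or later. It does not say that this grouping is crossed with naCRT/dCRT, and gives no at-risk denominator for the later events. No person-time, censored or common-window summary is planned.

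**The concern.** Two percentages will be printed for naCRT and dCRT, and readers will compare them. Each is a count of patients with an SAE divided by all attempters, but the time in which an SAE could be counted differs.

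- **Length.** If the aimed-for timing is kept, a naCRT patient is observed for hours to a week, and a dCRT patient for about two weeks.
- **Content.** Where response endoscopy is routine, it usually falls inside the dCRT window. SAEs count regardless of causality (Protocol 11.1), and Protocol 11.4 lists bleeding from a biopsy site among the device effects. The naCRT window closes when that group's next planned procedure, surgery, takes place.

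Both differences push the same way. A lower naCRT figure could be read as evidence that the test is riskier after dCRT, which is the population the surveillance programme is meant for, when it reflects only how long each group was watched.

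**Working it through.** **1. The plan's own figure.** The only design figure is the precision of the completion rate: 1.96 × √(0.7 × 0.3 / 50) = 0.127, which agrees with the stated ±13%. It does not bear on safety. The documents give no SAE rate, no naCRT/dCRT split and no surgery intervals, so the sizes below are illustrations under stated assumptions.

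**2. Direction.** Let R be the same two-week SAE risk in both groups. A naCRT patient operated on at day d < 14 contributes only the risk up to day d, which cannot exceed R. The expected naCRT percentage is therefore at most R, with equality if nobody is operated on within two weeks or no risk remains after surgery.

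**3. Size when part of the risk falls on the procedure day.** Assume a fraction f of two-week SAEs occurs on the procedure day before any surgery, and the rest is uniform over 14 days. The share outside the naCRT window is (1 − f)(14 − d)/14. The last column takes R = 10%, with half of surgery on day 0 and half on day 7.

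| f | share missed, d = 0 | share missed, d = 7 | mean share | naCRT shown (dCRT 10%) |
|---|---|---|---|---|
| 0.3 | 0.70 | 0.35 | 0.525 | 4.75% |
| 0.5 | 0.50 | 0.25 | 0.375 | 6.25% |
| 0.8 | 0.20 | 0.10 | 0.150 | 8.5% |

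No endoscopy SAEs are added to dCRT here.

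**4. Size under a constant hazard.** With h = −ln(1 − 0.10)/14 = 0.00753 per day, naCRT risk to day d is 1 − exp(−h × d).
- Day 7: 5.1%, ratio to dCRT 0.51.
- Day 3: 2.2%, ratio 0.22.
- Day 1: 0.75%, ratio 0.08.
- For two-week risks from 5% to 20%, the day-7 ratio is 0.51 to 0.53.

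**5. Where it shrinks or vanishes.** The ratio is f + (1 − f) × d/14.
- f = 0.9 and d = 7: 0.95.
- f = 1: 1.00.
- f = 0, half of naCRT operated on at day 7 and the rest after day 14: 0.5 × 0.5 + 0.5 × 1 = 0.75.

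**6. What one trial would show.** Assume 25 patients per group, R = 10%, a constant hazard and day-7 surgery for all naCRT patients. By exact binomial calculation, naCRT shows the lower percentage with probability 0.65 and the higher with 0.17. With equal windows each probability is 0.405.

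**7. Does exposure-based reporting remove it?** Under a constant hazard both groups show 0.75 SAE patients per 100 patient-days. A single whole-window rate can overcorrect when events cluster early. With f = 0.5, R = 10% and day-7 surgery, per 100 patients and ignoring time lost after an event:
- Whole window: naCRT 7.5/700 = 1.07 per 100 patient-days; dCRT 10/1,400 = 0.71.
- Later events only: naCRT 2.5/700 = 0.36; dCRT 5/1,400 = 0.36.

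So the rate should be read together with the split between procedure-day and later events.

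**The case against.** The case for leaving the plan alone has substance.

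- **No comparison is planned.** The table is descriptive, the safety endpoint is not group-specific, and neither the stopping rule nor the criterion of a completion rate above 70% uses a difference between groups. This stands, and limits the consequence to how the table is read.
- **Closing follow-up at surgery is deliberate.** Protocol 5.3 explains that the effect on the oesophagus no longer applies once it is removed. This stands. The defect is not the cut-off, but keeping an untruncated denominator and printing the result beside dCRT.
- **It is disclosed.** SAP 5.5, 6.3 and 6.4 mention the shortened follow-up. Disclosure does not change the percentages, and SAP 5.5 does not clearly give the interview counts by group.
- **Many device events are procedural.** Detachment, failed retrieval, airway obstruction and laceration would mostly occur on the day, so a high f is plausible for them and the gap would be small.
- **Counts may be tiny.** At an assumed 2% risk, f = 0.5 and 25 per group, with the surgery mix of step 3, expected patients with an SAE are 25 × 0.02 = 0.5 in dCRT and 0.5 × 0.625 ≈ 0.3 in naCRT. Neither figure would support a conclusion about groups.
- **Endoscopy complications are partly separable.** Causality is assessed for every event, although the biopsy-site bleeding item blurs this.

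**Conclusion.** The point holds as a reporting defect in a descriptive table. At equal underlying risk the expected naCRT SAE percentage is equal to or below the dCRT percentage. Under the assumptions in step 3, a true 10% would appear as 4.75% to 8.5% in naCRT. The actual size depends on surgery dates and on the share of SAEs on the procedure day, neither of which the documents give.

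A reader might infer several stronger statements that the documents do not support.

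- **That naCRT must look safer by construction.** Surgery timing is an aim, the effect can be nil, true risks may differ between groups, and even in the step 6 scenario naCRT shows the higher percentage with probability 0.17.
- **That some minimum share of events, such as 10%, is always missed.** That floor comes from stopping at f = 0.8 and day 7. At f = 0.9 and day 7 the share is 5%, and at f = 1 it is zero.
- **That dCRT follow-up always includes an endoscopy.** It does so only where response endoscopy is routine, and then usually.
- **That the plan will count operated naCRT patients as event-free in later rows by group.** SAP 6.2.2 does not say that the day/later grouping is crossed with treatment group.

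**What to change.** In the SAP 6.2.2 table of SAEs, SADEs and USADEs by group:

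1. Beside the crude percentage, report patient-days observed in each group and the SAE rate per patient-day, or the cumulative incidence with follow-up ending (censored) at surgery.
2. Show procedure-day events by group. For later events, use as denominator only patients not yet operated on, with their patient-days. The patient-days matter because a patient operated on at day 7 is at risk for only half of the later period.
3. Footnote that the crude two-week percentages cover unequal windows and are not for comparison between groups. Where the date is known, flag dCRT SAEs that occurred after a response endoscopy.

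Ending both windows at the next planned oesophageal procedure would not give a common window: dCRT patients without an endoscopy would still run two weeks, and those with a same-day endoscopy would be reduced to hours.

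The cost is SAP wording and some table work, with no new patients, visits or procedures. The surgery date is already needed to close the reporting period. Endoscopy dates are less certain, since Protocol 7.1 asks only for pathology and surgical reports, hence the condition in item 3. The rates will be sparse and imprecise, and same-day surgery leaves little or no later naCRT follow-up to report.

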5.3 Evaluations during the study

Evaluations on day 1

On the day the intervention is given:

- Dysphagia score (Mellow Scale)
- Research bloods (optional) if not already collected at Pre-study intervention

Post procedure:

- Assessment of immediate complications (safety monitoring)
- Questionnaire (participants complete post procedure in clinic, or return by post to their recruiting hospital if this cannot be achieved)

Telephone Follow-up evaluations (End of study)

No face-to-face follow-up visit is planned beyond the Cytosponge™ procedure, however patients will have telephone appointments with a qualified member of the research team as per summary of events (week 1 and week 2) to review concomitant medications, dysphagia score and assess for any complications. This can be completed in person if deemed appropriate by the local study team. This is only applicable for participants that have received definitive CRT (not for surgery), or for participants who have received neo-adjuvant CRT, if these times are prior to surgery. This is because the trial is exploring the Cytosponge™ effect on the oesophagus, which will no longer be applicable after this has been removed in surgery.

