11.8 Reporting Adverse Events on the CRF

All AEs, including Serious AEs must be recorded on the case report forms (CRF) for that patient (unless otherwise specified in section 11.9. The information provided will include date of onset, event diagnosis (if known) or sign/symptom, severity, time course, duration and outcome and relationship of the AE to device. Any concomitant medications or any other therapy used to treat the event must be listed. The Investigator will provide an "other" cause for serious AEs considered to be unrelated to the study device. Sites should ensure data entered into the CRF is consistent with the SAE report information where applicable.

Each separate AE episode must be recorded. For example, if an AE resolves completely or resolves to baseline and then recurs or worsens again, this must be recorded as a separate AE. For AEs to be considered intermittent, the events must be of similar nature and severity.

AEs may be spontaneously reported by the patient and/or in response to an open question from study personnel or revealed by observation, physical examination, or other diagnostic procedures. Any clinically relevant deterioration in laboratory assessments or other clinical finding is considered an AE.

AEs which are serious must be reported to OCTO from the time of Cytosponge™ administration until the participant completes the study at the Two Week Telephone Follow Up appointment. If a participant receives surgery prior to this point, the safety reporting period will be up until the participant receives surgery (see section 5.3, Telephone Follow-Up Evaluations (End of Study)). Should an Investigator become aware of any study intervention related Serious Adverse Device Effects (SADEs) following the Two Week Telephone Follow Up, these must also be reported to OCTO.

Terms and Grading of Events

The NCI CTCAE Version 4.0 (currently up to Version 4.03) must be used by the site for grades; the events will be coded in-house by the Pharmacovigilance team using MedDRA and where possible using the Lowest Level Terms provided. Where indicated on the SAE form, provide the severity grade, and the worst grade recorded.

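### AE and ADE percentages are planned without a dCRT/naCRT split, so they pool patients observed for about two weeks with patients observed only until surgery

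*SAP*

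**What the plan says.** SAP 6.2.2 (Safety) treats two sets of events differently. For serious events, "the number and percentage of patients experiencing SAEs overall, will be presented by treatment group (naCRT/dCRT"). For all AEs and ADEs, the next paragraph says: "It is intended that the number and percentage of patients experiencing AEs and ADEs will be presented overall and according to causality (treatment-relatedness"). The further AE splits are optional: grade, system organ class, and day of procedure versus later. CRT group is not among them, and SAP 6.4 limits the pre-specified subgroup analysis to the completion rate.

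These tables use the safety population, which SAP 4.2 defines as "all participants who attempted to swallow the Cytosponge™", with no condition on length of observation.

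The safety window runs from administration to the two-week call, with one exception in SAP 6.1.2: "If a participant undergoes surgery prior to their two week follow up visit, then their safety reporting period continues until the time of surgery". Protocol section 11 says the same. On timing, a footnote to the Protocol's Summary of Events reads: "If patient has received neo-adjuvant CRT, aim to perform Cytosponge™ on the same day or within a week prior to surgery". Protocol 8.3 adds that after naCRT "the procedure should be performed on the day of surgery prior to the operation (but this is not mandatory").

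**The concern.** Two groups with planned windows of different length share one denominator. A naCRT patient operated on the same day contributes hours of observation. A dCRT patient contributes up to the two-week call, scheduled at two weeks plus or minus two days. In a crude percentage, time after surgery counts as time without an event.

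The study does look for later effects. The week 1 and week 2 contacts exist "to review concomitant medications, dysphagia score and assess for any complications", and Protocol 11.8 states: "Any clinically relevant deterioration in laboratory assessments or other clinical finding is considered an AE". A worsening dysphagia score could therefore become an AE in a dCRT patient, while a naCRT patient already operated on has no call at which it could be found.

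What is at stake is the usefulness of the AE/ADE tables for the intended setting. The Protocol (1.3) and SAP (2.1) look ahead to surveillance after dCRT, where the oesophagus stays in place, and Protocol 1.3 says there are no safety data for the device in carcinoma patients after dCRT. The planned tables would not show the two-week AE/ADE percentage for that group.

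**Working it through.** **Plan's own figure.** The plan gives none on this point. The number of patients used below, 50, comes from SAP 3.3. The precision stated there reproduces: 1.96 × √(0.7 × 0.3/50) = 0.127, that is ±13%. It is not in dispute.

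**Observation windows, from the documents.**
- dCRT, no surgery: day 1 to the two-week call, about 14 days.
- naCRT, timed as the protocol aims: 0 to 7 days, ending at surgery.
- naCRT, operated on after the two-week call: full window, no truncation.

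**Assumptions, because the documents give neither naCRT numbers nor event timing.**
- R: two-week risk of at least one AE (or ADE) in patients who keep their oesophagus.
- m: number of the 50 who are naCRT patients operated on before the two-week call.
- s: share of affected patients whose first event would fall after the time of surgery.
- k: naCRT risk divided by dCRT risk.

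**Equal risk and timing (k = 1).** Pooled = [(50 − m)R + mR(1 − s)]/50 = R × [1 − (m/50)s].

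| m | s = 0.10 | s = 0.25 | s = 0.50 |
|---|---|---|---|
| 5 | 0.99 | 0.975 | 0.95 |
| 10 | 0.98 | 0.95 | 0.90 |
| 25 | 0.95 | 0.875 | 0.75 |

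The factor is 1.00 if s = 0. With R assumed to be 20%:
- m = 10, s = 0.25: (40 × 0.20 + 10 × 0.20 × 0.75)/50 = (8 + 1.5)/50 = 19.0%.
- m = 25, s = 0.50: (25 × 0.20 + 25 × 0.20 × 0.50)/50 = (5 + 2.5)/50 = 15.0%. The dCRT column alone would show 5/25 = 20%.

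**Unequal risk.** Pooled = R × [(50 − m) + mk(1 − s)]/50. This equals R when k(1 − s) = 1, that is k = 1/(1 − s), whatever m is. The break-even ratios are 1.11 (s = 0.10), 1.33 (s = 0.25) and 2.00 (s = 0.50). With R = 20%, m = 20 and s = 0.50:
- k = 1: 0.6 × 20% + 0.4 × 20% × 0.5 = 16.0%.
- k = 2: 20.0%.
- k = 3: 24.0%.

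So the pooled figure can fall below, match or exceed the dCRT risk.

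**Optional later-event rows.** If k₁ naCRT patients are operated on the same day and all attempters remain in the denominator, the later-event percentage is multiplied by (50 − k₁)/50 under equal risk. That is 0.90, 0.80 and 0.50 for k₁ = 5, 10 and 25. This row is diluted more than the overall one.

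**Day-of-procedure rows.** Same-day surgery ends observation within day 1, so these rows are also shortened for naCRT patients, to a lesser degree.

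**The case against.** The strongest reply is that the window is a deliberate definition. Protocol 5.3 explains that the trial studies the device's effect on the oesophagus, which ceases to apply once it is removed. SAP 6.3 and 6.4 disclose the truncation, and SAP 5.5 reports how many patients had the calls. No passage presents the pooled percentage as a two-week risk after dCRT. This stands as a defence of ending observation at surgery. It does not justify keeping patients without an oesophagus in the denominator for later events, and neither the disclosure nor the interview counts change that denominator.

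Second, the information may be recoverable: Protocol section 18 promises data listings, SAP section 1 leaves room for exploratory analysis, and the AE wording is an intention that forbids nothing. That is true, but a reader of the planned tables would still not see the dCRT figure.

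Third, the effect may be very small. Protocol 1.3 reports only temporary sore throat as a device-related adverse effect, and most risks listed in 11.4 are acute, so s may be low for ADEs. Moving from 20.0% to 19.0% is half a patient in 50, while a Wilson 95% interval for 10/50 runs from about 11% to 33%. This stands, and it limits the weight of the point.

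A reader might infer that the pooled percentages must understate dCRT risk whenever some events would fall after surgery. The documents do not support that: it also requires naCRT risk to be below 1/(1 − s) times the dCRT risk, and nothing in them establishes equal risk. A reader might also take day-of-procedure figures to be untouched. Protocol 8.3 points naCRT patients to the day of surgery, so they are not wholly so.

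**Conclusion.** The point holds as a minor reporting gap. The planned AE and ADE percentages mix unequal observation windows and do not describe two-week risk in patients who keep their oesophagus. Under equal risk and timing they are too low by the factor 1 − (m/50)s, which runs from 0.99 to 0.75 over the values tabulated. Both m and s are assumptions, and the direction depends on the unknown ratio of risks. Truncation applies only to naCRT patients operated on before the two-week call, which is what the protocol aims for but does not require.

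It would go too far to infer that the trial's safety conclusion or its decisions are compromised. The defined safety endpoint is serious procedure-related effects, and SAE percentages are already planned by CRT group. The stopping rule and the trigger for a TMG meeting are counts of serious complications. The go-ahead rule rests on completion above 70% and on the primary and secondary objectives, with no threshold on AE or ADE percentages.

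**What to change.** Amend SAP 6.2.2 as follows:

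1. Present AEs and ADEs by dCRT and naCRT as well as overall, including the day-of-procedure rows, as already planned for SAEs.
2. For later-event rows, use as denominator the patients still under observation after day 1.
3. Because patients operated on before the two-week call are only partly observed, show by group the numbers observed at weeks 1 and 2, and the days of follow-up to surgery or the two-week call.

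The main cost is revised table shells. CRT group is already tabulated (SAP 5.3, Table 2) and AE onset dates are recorded (Protocol 11.8). The surgery date must be available. The Protocol does not list it as a CRF item, but the safety window cannot be applied without it, and Protocol 7.1 provides for surgical reports to go to the Trial Office. The price is smaller denominators and less precision in each group. If analysis has already begun, the tables can be added and the change described in the final report, as SAP section 1 provides for deviations.
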